### **Evaluation of non-measurable bone disease**

Bone scans obtained after the baseline evaluation will be used to evaluate post-treatment changes. Bone scans obtained will be evaluated as either “no new lesions” or “new lesions” on the tumor measurement forms. Progression is defined as the appearance of 2 or more new lesions.

**PSAWG2 Criteria for Bone Scan Evaluation:** For the first scheduled reassessment: New lesions at the first scheduled evaluation (8 weeks) will require a confirmatory bone scan 6 or more weeks later. If no new lesions are observed on the confirmatory bone scan, study therapy is continued. If additional new lesions (a minimum of 2 more additional new lesions) are observed, then the patient has experienced progression. Progression in this situation is dated as the time of the first reassessment scan.

For subsequent scheduled reassessments: If no new lesions are observed, study therapy will continue. If new lesions are observed, this is evidence of disease progression. Date of progression is the date at which the scan was obtained.

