#### **7.3.1.2 Methods for Evaluation of Non-Measurable Disease**

PSA levels will be monitored monthly.

Bone scans obtained after the baseline evaluation will be used to evaluate post-treatment changes. Outcome is listed as new lesions or no new lesions. Progression is defined as the appearance of 2 or more new lesions. This is based on the PCWG2 criteria in standard practice for trials in metastatic CRPC.

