#### Time to confirmed development of $\geq 2$ new bone lesions

Time to development of  $\geq 2$  new bone lesions, defined as the time interval between the date of treatment initiation and the date of documented new lesions. Bone scans will be performed at week 8, 16, 24, and every 12 weeks thereafter; evaluation criteria is defined by the PSAWG2 criteria for bone scan evaluation. The time will be 'backdated' to when the  $\geq 2$  new lesions were detected if a second scan is done to confirm progression.

Kaplan-Meier methods will be used to estimate the median time to development of  $\geq 2$  new bone scans with a 95% confidence interval.

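### Bone scans are recorded only as new lesions or no new lesions, while bone progression is defined by lesion counts, and the operative sentences in section 7.3 leave out the threshold of 2.

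*Combined protocol and SAP*

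**What the plan says.** **Recording.** Section 7.3 (Evaluation of non-measurable bone disease): "Bone scans obtained will be evaluated as either “no new lesions” or “new lesions” on the tumor measurement forms". Section 7.3.1.2: "Outcome is listed as new lesions or no new lesions".

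**Threshold.** Both sections then define progression by number; in 7.3, "Progression is defined as the appearance of 2 or more new lesions". Section 2.4.1 writes a rule of 2 or more new lesions, then 2 or more additional ones, into the primary endpoint.

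**First reassessment (7.3).** "New lesions at the first scheduled evaluation (8 weeks) will require a confirmatory bone scan 6 or more weeks later". Then: "If additional new lesions (a minimum of 2 more additional new lesions) are observed, then the patient has experienced progression". On dating: "Progression in this situation is dated as the time of the first reassessment scan". If the confirmatory scan shows no new lesions, it is not progression.

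**Later scans (7.3).** New lesions are taken as evidence of progression, dated to that scan. No number is given.

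**Secondary bone endpoint (8.4.3).** "The time will be 'backdated' to when the" 2 or more new lesions were detected. Scans fall at weeks 8, 16 and 24, then every 12 weeks.

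**Confirmation interval.** Section 7.3 requires 6 or more weeks. Section 8.4.2 requires 12 or more weeks. Section 2.4.1 gives no interval between scans and refers instead to 12 weeks after the start of treatment.

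**The concern.** A two-level field carries less information than the rule applied to it. The rule needs the number of new lesions against baseline and the number of additional lesions against the first on-treatment scan. The plan describes neither as recorded. The nearest lesion-level item, in the non-target lesion paragraph of 7.3, is the presence or absence of lesions listed at baseline, which gives no count of new ones.

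The same gap appears in the rule itself. Section 7.3 states the threshold of 2 and then drops it from the sentences that a reader would follow at week 8 and at later scans.

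Inclusion criterion 7 requires at least one bone metastasis, so bone scans bear on the primary endpoint in every patient. The week 8 and week 16 scans are the scheduled bone scans up to the 16-week decision point. If sites resolve the ambiguity differently, or an analyst works from the recorded category alone, event status and event dates will depend on choices that the plan does not state.

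**Working it through.** **1. Two-scan records against the written rule**

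Inputs: scans at weeks 8 and 16 (8.4.3), two-category recording (7.3, 7.3.1.2), and the confirmation and dating rules of 7.3. Week 16 is 16 − 8 = 8 weeks after week 8, so it satisfies the 6-week interval in 7.3. It does not satisfy the 12-week interval in 8.4.2.

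| New at week 8, additional at week 16 | Recorded | Result under the text |
|---|---|---|
| 2, then 0 | new, no new | Not progression (7.3) |
| 2, then 2 | new, new | Progression dated week 8 (7.3 and 8.4.3) |
| 2, then 1 | new, new | No outcome in the confirmation rule; progression if the later-scan sentence is applied to week 16 |
| 1, then 2 | new, new | Literal 7.3: progression dated week 8. Backdating rule of 8.4.3: week 16, the first scan with 2 or more new lesions against baseline |
| 0, then 1 | no new, new | Literal later-scan sentence: progression at week 16. Threshold of 2: not progression |

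The second, third and fourth rows share one recorded code. The fourth and fifth rows give different answers under different sentences of the plan. These patterns show the logic; the documents give no frequencies for them.

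**2. Which estimate each problem touches**

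- 1-then-2: dating to week 8 instead of week 16 moves rPFS by 16 − 8 = 8 weeks for that patient, and so affects the Kaplan-Meier estimates. If a week 16 scan event counts as progression by 16 weeks, the patient is a failure either way and the 16-week classification does not change.
- A single new or additional lesion at week 16: scoring it as an event changes the 16-week classification, and therefore the primary proportion.

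**3. Reproducing the design (8.2.1)**

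Inputs: 18 patients in stage 1, stop at 10 or fewer progression-free; 54 in total, reject at 36 or more; null 0.55, alternative 0.75.

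P(stop) = P(X₁ ≤ 10), with X₁ ~ Bin(18, p).

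P(reject) = Σ over x = 11 to 18 of P(X₁ = x) × P(X₂ ≥ 36 − x), with X₂ ~ Bin(36, p).

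- p = 0.55: early stopping 0.6085, type I error 0.0477 (plan: 60.9% and 0.048).
- p = 0.75: early stopping 0.057, power 0.9007 (plan: 90.0%).

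The plan's figures reproduce.

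**4. Illustration of sensitivity**

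Assume that some patients who would otherwise count as progression-free are scored as events on a single lesion and have no other event by week 16. The share is assumed.

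| Drop from 0.75 | Proportion classified progression-free | Patients of 54 | Power | Early stopping |
|---|---|---|---|---|
| 0 | 0.75 | 0 | 0.901 | 5.7% |
| 3 points | 0.72 | 0.03 × 54 = 1.6 | 0.797 | 10.1% |
| 5 points | 0.70 | 0.05 × 54 = 2.7 | 0.702 | 14.1% |
| 8 points | 0.67 | 0.08 × 54 = 4.3 | 0.532 | 21.4% |

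The base matters. If the 5% is a share of the truly progression-free patients, the proportion is 0.75 × 0.95 = 0.7125 and power is 0.764.

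The opposite error is also possible. If 5% of truly progressed patients are classed as progression-free because the count cannot be shown, the null proportion becomes 0.55 + 0.45 × 0.05 = 0.5725 and type I error rises from 0.048 to 0.090.

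**The case against.** The tumor measurement form is not in the documents. Saying that scans are evaluated in two categories does not say that the form holds nothing else. A CRF completion manual is listed in Appendix 3, and section 9.7 keeps source documents and requires the CRFs to match them. Readers may also count lesions and apply the rule themselves, so that progression is entered as a determination. All of this stands. A reader might infer that bone progression cannot be derived at all; the documents do not support that. They show only that the plan does not provide for capturing the counts and that the recorded category alone is insufficient.

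A second tempting inference is that scoring 2-then-1 as progression is a false failure. Section 7.3 does not settle this. Its confirmation rule is silent on exactly one additional lesion, while its later-scan sentence could make it progression. The defect is the missing assignment, not a proven error in one direction.

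Third, the misdating of 1-then-2 depends on reading new lesions in the week 8 sentence as including a single lesion. Section 2.4.1 starts confirmation from 2 or more, and so could be used to read a threshold into 7.3. That would remove the week 8 misdating but leave a single new lesion without a clear recorded category and the additional count still uncaptured. Nor should one infer that the secondary bone endpoint is misdated: its own backdating sentence in 8.4.3 prevents that, provided the count is known.

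Finally, the rates in the illustration are not from the documents, and count fields alone would not resolve the conflicting confirmation wording in 2.4.1, 7.3 and 8.4.2.

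**Conclusion.** The concern holds as a conflict between stated rules, not merely as missing detail. The plan defines bone progression by counts, describes a recorded outcome without counts, and omits the threshold from the operative sentences in 7.3.

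Three consequences follow from the text:

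- 2-then-2, 2-then-1 and 1-then-2 cannot be separated from the recorded outcome without source reports.
- A literal reading of 7.3 dates a 1-then-2 patient to a scan below the threshold, and makes one new lesion at a later scan an event.
- Exactly one additional lesion on the confirmatory scan has no outcome in the confirmation rule.

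The dating effect is 8 weeks of rPFS per such patient. It leaves the 16-week classification unchanged if a week 16 scan event counts as progression by 16 weeks. A single lesion scored as an event at week 16 does bear on the primary proportion. The size of that effect is unknown: the fall in power to 0.80, 0.70 or 0.53 assumes drops of 3, 5 or 8 percentage points and no other event by week 16 in those patients. It shows how sensitive the design is and is not an estimate of loss. The case for the change does not depend on those figures.

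**What to change.** 1. At every bone scan, record the number and site of new lesions against baseline, and of additional lesions against the first on-treatment scan. Derive bone progression for the endpoints from these counts.
2. For endpoint scoring, put the threshold of 2 or more into the week 8 and later-scan sentences of section 7.3.
3. State how exactly one additional lesion on the confirmatory scan is classified.
4. Date progression to the first reassessment scan only if that scan itself showed 2 or more new lesions, as section 8.4.3 already does for the secondary bone endpoint.
5. Reconcile the confirmation wording in sections 2.4.1, 7.3, 8.4.2 and 8.4.3, including the interval and whether the week 16 scan can confirm a week 8 finding.

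The cost is two numeric fields, with lesion site, on the tumor measurement form and a few sentences of text. No extra scans are needed, and no extra reads, since applying the count rule already requires readers to count lesions.

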#### **7.3.1.1 Methods for Evaluation of Measurable Disease**

All measurements will be taken and recorded in metric notation using a ruler or calipers. All baseline evaluations will be performed as closely as possible to the beginning of treatment and never more than 28 days before the beginning of the treatment, with the exception of imaging which may be performed up to 42 days before the beginning of the treatment.

The same method of assessment and the same technique will be used to characterize each identified and reported lesion at baseline and during follow-up.

#### **7.3.1.2 Methods for Evaluation of Non-Measurable Disease**

PSA levels will be monitored monthly.

Bone scans obtained after the baseline evaluation will be used to evaluate post-treatment changes. Outcome is listed as new lesions or no new lesions. Progression is defined as the appearance of 2 or more new lesions. This is based on the PCWG2 criteria in standard practice for trials in metastatic CRPC.

#### **7.3.1.3 Response Criteria**

##### **Evaluation of Target Lesions**

###### **Complete Response (CR)**

Disappearance of all target lesions, determined by two separate observations conducted not less than 4 weeks apart. Any pathological lymph nodes (whether target or non-target)

must have reduction in short axis to <10 mm (the sum may not be “0” if there are target nodes). There can be no appearance of new lesions.

**Partial Response (PR)**

At least a 30% decrease in the sum of the longest diameter (LD) of target lesions, taking as reference the baseline sum LD. There can be no appearance of new lesions.

**Progressive Disease (PD)**

At least a 20% increase in the sum of the SLD of target lesions, taking as reference the smallest sum SLD recorded since the treatment started and minimum 5 mm increase over the nadir, or the appearance of one or more new lesions.

**Stable Disease (SD)**

Neither sufficient shrinkage to qualify for PR nor sufficient increase to qualify for PD, taking as reference the smallest sum LD since the treatment started.

**Evaluation of Non-Target Lesions**

**Complete Response (CR)**

Disappearance of all non-target lesions and normalization of tumor marker level. All lymph nodes must be non-pathological in size (< 10 mm short axis).

**Incomplete Response/Stable Disease (SD)**

Persistence of one or more non-target lesion(s) and/or maintenance of tumor marker level above the normal limits.

**Progressive Disease (PD)**

Appearance of one or more new lesions and/or unequivocal progression of existing non-target lesions.

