### **2.4 Endpoints**

#### **2.4.1 Primary Endpoints**

Radiographic progression free survival (rPFS). This is defined from study start until one of the following events occurs:

- $\geq 2$  new bone lesions on Technetium bone scan. If  $\geq 2$  new lesions are detected at or 12 weeks following initiation of treatment, progression must be confirmed by the presence of  $\geq 2$  or more additional lesions to rule out bone scan flare as a cause of the radiographic changes.

- RECIST-defined tumor progression.
- Clinical deterioration requiring a change in prostate cancer therapy, or at clinician discretion
- Surgery or Radiation to treat a prostate cancer related indication
- Death from any cause.

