### 7.3 Disease Parameters

#### **Measurable disease**

Measurable disease is defined as lesions (or tumors) that can be accurately measured in at least one dimension (longest diameter to be recorded) with a minimum size of 10mm by CT scan (irrespective of scanner type) or bone scan. All tumor measurements will be recorded in millimeters or decimal fractions of centimeters. Previously irradiated lesions are considered non-measurable except in cases of documented progression of the lesion since the completion of radiation therapy.

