#### **Non-target lesions**

All other lesions (or sites of disease) including any measurable lesions over and above the 5 target lesions should be identified as non-target lesions and should also be recorded at baseline. It is possible to record multiple non-target lesions involving the same organ as a single item on the case record form (e.g. "multiple enlarged pelvic lymph nodes" or "multiple liver metastases"). Bone lesions may be measurable if  $\geq 1$  cm on MRI. Measurements of these lesions are not required, but the presence or absence of each will be noted throughout follow-up.

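### The primary endpoint is inconsistent on bone: a patient with exactly one new bone lesion at 16 weeks can be classified as progressed or as progression-free

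*Combined protocol and SAP*

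**What the plan says.** **RECIST side.** In Section 7.3.1.3, progression of target lesions includes "or the appearance of one or more new lesions". Progression of non-target lesions is "Appearance of one or more new lesions and/or unequivocal progression of existing non-target lesions". The best-overall-response table scores any new lesion as PD. None of the three sets bone apart.

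Bone also falls inside this framework. The measurable-disease definition in Section 7.3 admits lesions "with a minimum size of 10mm by CT scan (irrespective of scanner type) or bone scan". The non-target definition reads "All other lesions (or sites of disease) including any measurable lesions over and above the 5 target lesions should be identified as non-target lesions", and goes on to discuss bone lesions on MRI.

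**Bone-scan side.** Section 7.3.1.2 says "Progression is defined as the appearance of 2 or more new lesions" and adds "This is based on the PCWG2 criteria in standard practice for trials in metastatic CRPC". The bone-disease subsection of Section 7.3 opens with the same two-lesion definition and requires a confirmatory scan for new lesions at the first (week 8) reassessment. For later reassessments it says only "If new lesions are observed, this is evidence of disease progression".

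**Endpoint side.** Section 2.4.1 lists at least two new bone lesions, with confirmation of early ones, and separately "RECIST-defined tumor progression". The event list in Section 8.4.2, attached to the proportion free of radiographic progression at 16 weeks, has the same two items, and RECIST is again unrestricted. The narrative rPFS paragraph just below that list limits RECIST to soft tissue, under modified criteria that are not defined, and keeps at least two new lesions for bone.

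**The concern.** Two careful readers could classify the same patient differently. With exactly one new bone lesion and nothing else, the RECIST text gives PD, and PD is an endpoint event in Section 2.4.1 and in the Section 8.4.2 list. By the two-lesion rule, the same patient has not progressed.

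The trial is decided by counting patients classified as progression-free at 16 weeks, at 18 and at 54 patients. Inclusion criterion 7 requires at least one bone metastasis, so the question can arise for anyone enrolled. The week-16 scan is also the one where the bone text itself is least clear. Under the schedule in Section 8.4.3 (weeks 8, 16, 24, then every 12 weeks) it is a later reassessment, where the wording gives no lesion count.

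**Working it through.** **Step 1. One patient, each rule.** Take a patient whose week-16 bone scan shows exactly one new lesion, with no soft-tissue change and no other event.

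| Text | Rule | Result |
|---|---|---|
| 7.3.1.3, target, non-target and best-response table | one or more new lesions, any site | progressed |
| 7.3 bone disease, opening definition | two or more new bone lesions | not progressed |
| 7.3 bone disease, later reassessments | new lesions, no count given | unclear |
| 7.3.1.2 | two or more new bone lesions | not progressed |
| 2.4.1 and 8.4.2 list, bone item | at least two new bone lesions | not an event |
| 2.4.1 and 8.4.2 list, RECIST item | RECIST progression, any site | event, through 7.3.1.3 |
| 8.4.2 narrative | RECIST in soft tissue; at least two for bone | not an event |

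The answer depends on the text followed.

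**Step 2. Reproduce the design.** Inputs from Section 8.2.1: n1 = 18, stop if 10 or fewer are progression-free; n = 54, reject if 36 or more; null 55%, alternative 75%. With X1 ~ Bin(18, p) and X2 ~ Bin(36, p):

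- P(stop early) = P(X1 ≤ 10)
- P(reject) = Σ over x = 11 to 18 of P(X1 = x) · P(X2 ≥ 36 − x)

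| Quantity | Stated | Recomputed |
|---|---|---|
| P(stop early), p = 0.55 | 60.9% | 0.6085 |
| Type I error, p = 0.55 | 0.048 | 0.0477 |
| Power, p = 0.75 | 90.0% | 0.9007 |

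The design arithmetic is sound. The question is only what is being counted.

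**Step 3. Sensitivity, with an assumed rate.** No document figure says how many patients would have exactly one new bone lesion by week 16 and no other event. Let d be that share.

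*Direction A: the 75% alternative was set under the two-lesion reading and patients are scored under the one-lesion reading.* The working rate is 0.75 − d.

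| d | Rate | P(reject) |
|---|---|---|
| 0 | 0.75 | 0.901 |
| 0.03 | 0.72 | 0.797 |
| 0.05 | 0.70 | 0.702 |
| 0.10 | 0.65 | 0.415 |

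*Direction B: the 55% null was set under the one-lesion reading and patients are scored under the two-lesion reading.* An ineffective drug then shows 0.55 + d.

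| d | Rate | P(reject) |
|---|---|---|
| 0 | 0.55 | 0.048 |
| 0.02 | 0.57 | 0.084 |
| 0.05 | 0.60 | 0.172 |

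The plan does not say which reading lies behind 55% or 75%, so neither direction can be excluded.

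**The case against.** The strongest reply is that the intended split is already visible. The Section 8.4.2 narrative confines RECIST to soft tissue. Inclusion criterion 5 separates soft-tissue progression by modified RECIST from at least two new lesions on bone scan. Inclusion criterion 6 repeats a split of RECIST for soft tissue and modified PCWG2 for bone in each of items a to d. The bone subsection of Section 7.3 opens with the two-lesion definition for all post-baseline scans, so its later-scan sentence can be read as inheriting that count. On this view the specific bone rule governs bone, and the RECIST text is generic wording.

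Most of that stands as evidence of intent. It does not remove the conflict. The narrative defines the time-to-event rPFS, whereas the unrestricted list above it is the one attached to the 16-week proportion that is tested. The soft-tissue limit is missing from Section 2.4.1 and from the response criteria, and Section 7.3 places bone inside the RECIST lesion definitions.

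A reader might go further and infer that the two-lesion and confirmation safeguards can never operate, because any new bone lesion, flare included, would first trigger RECIST progression. The documents do not support that. It follows only if Section 2.4.1, the response criteria and the Section 8.4.2 list are read literally and the Section 8.4.2 narrative is set aside. Under the narrative, the two-lesion rule works as written.

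**Conclusion.** The inconsistency is real and lies in the primary endpoint. With exactly one new bone lesion, classification at 16 weeks depends on which part of the protocol is followed, and the later-scan wording in Section 7.3 adds to the doubt at that visit. It should be fixed. Because the intended split can be recognised elsewhere in the protocol, it is a defect of wording and not a failure of the design, whose stated operating characteristics reproduce.

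The contradiction rests on the text alone; its size does not. The fall in power to 80%, 70% or 41% needs 3, 5 or 10 points of reclassification, applied to all patients, with the 75% set under the two-lesion reading. The rise in rejection probability to 0.084 or 0.172 needs 2 or 5 points and a 55% null set under the one-lesion reading. A reader might take the power loss as the expected effect, but no document figure supports any of these rates, and the error can run in either direction.

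**What to change.** For the endpoint, add one governing statement that RECIST progression applies to soft-tissue (non-bone) disease and that bone is assessed only by the bone-scan criteria. This matches the split already in the Section 8.4.2 narrative and the inclusion criteria. Carry it through:

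- Section 2.4.1, the RECIST item;
- Section 7.3, the measurable-disease and non-target definitions, so that bone does not remain inside RECIST measurement;
- Section 7.3.1.3, target and non-target progression and the best-overall-response table;
- Section 8.4.2, the RECIST item in the event list.

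Separately, reconcile the later-scan sentence in the bone-disease subsection of Section 7.3 with that subsection's opening definition and with Section 7.3.1.2. The same text also decides whether study therapy continues, so the sponsor must settle that rule; this review does not choose it.

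The cost is a wording amendment. It needs no additional visits, scans or patients, and leaves the 10-of-18 and 36-of-54 boundaries as they are.
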